Investigation of Activities of Muscles for Opening Eustachian Tube as Assessed by Simultaneous Electromyography and Tympanic Air Exchange Observations

NCT02667301 8-22-2020

Study Protocol

Protocol Title:	Investigation of Activities of Paratubal Muscles for Opening Eustachian Tube as Assessed by Simultaneous Electromyography and Tympanic Air Exchange Observations				
Principal Investigator:	 NAME: [name]. POSITION: ENT Specialist. TITLE: Associate Professor of Otorhinolaryngology, Director, Department of Otorhinolaryngology, Haseki Training and Research Hospital, Istanbul, Turkey. 				
Co-Investigators:	NAME: [name]. POSITION: Computer Specialist. TITLE: Professor, Computer Science and Engineering, College of Engineering, American University of Sharjah, United Arab Emirates. 4 SYG R&D, Istanbul, Turkey				
	Name: [name] Consultant, Department of Neurology, Haseki Training and Research Hospital, Istanbul, Turkey.				
	Name: [name], Resident of Otorhinolaryngology, Haseki Training and Research Hospital, Istanbul, Turkey.				
Study Coordinator:	None				
Population:	14 participants. All participants are above the age of 18 and have been diagnosed with Normal Eustachian function. All are of Turkish descent.				
Number of Sites:	Single site				
Study Duration:	Data evaluation period: 1 month. Total duration: 9 months				
Subject Duration:	45 minutes per subject.				
Funding:	FUNDING. This work was supported by TUBITAK, Turkish Scientific and Technological Research Organization under grant 1120070.				

General Information

Eustachian tube (ET) is a valve activated by levator and tensor veli palatine muscles and its duty is to equalize the pressure inside the tympanic cavity with outside pressure. Eustachian tube activation is commonly believed to be a sporadic activity which is initiated by swallowing or yawning action.

Background Information

Although there have been numerous EMG studies to understand the synergistic behavior of the two muscles, these studies never revealed the periodic nature of the activity and the tight relationship between the two muscle signals in terms of amplitude and delay.

Objectives

•

This study focuses on the relationship between eustachian tube openings at rest and paratubal muscle functions by observing transpalatal electromyography (EMG) and actual tubometric air exchange activity in healthy individuals with normal eustachian tube function.

Study Design

The design of the study was to be open and uncontrolled. The expected duration of the study was 9 months with 55 participants. The study was only able to recruit 14 participants.

- Using EMG to measure the activity of the LVP and TVP as mLVP and mTVP.
- The Tubometric device was deemed to be very accurate.
- The study was deemed to be very safe, the tip of the measurement devices that were to be inserted in the mouth and ear were 1.3x0.4 mm sterile subdermal monopolar electrodes and caused no discomfort. It was judged that there was no need for anesthesia.

Study Population

- Patients older than 18 years of age and diagnosed with Normal Eustachian function.
- Inclusion criteria included Individuals with normal eustachian function whose eardrum is intact and no hearing problems.
- Exclusion criteria included: Patients with severe septal deformities, nasal polyps and turbinate hypertrophy, adenoid and other nasopharyngeal mass cases were excluded. Patients with upper respiratory tract infections, acute otitis media, timpanosclerosis, otosclerosis and those who had previous ear surgery were not included in the study group
- Furthermore, those who met the inclusion criteria were inspected for any additional undesirable factors, such as Patients diagnosed with major depressive disorder, dysthymic disorder, bipolar disorder Patients with asthma, heart failure, cardiac arrhythmia, Raynaud's phenomenon, peripheral artery disease, insulin dependent diabetes mellitus, sexual dysfunction, hypertension, and renal failure. If they had any of the conditions/disorders, they were disqualified from the study.
- The approval of the Local Clinical Research Ethics Committee was obtained to conduct this study in Haseki Training and Research Hospital. The ETDQ7 questionnaire was filled out in patients who came to the Otorhinolaryngology clinic of Haseki hospital and had various ear complaints. Patients with a score of 14.5 points or greater in this quantitative test were accepted as potential "chronic eustachian dysfunction patients, and all of them were tested by our audiometrist in the audiology laboratory.

Study Procedures

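### Does the ETDQ-7 cut-off of 14.5 leave open who could enter a study of people with normal Eustachian function?

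*Protocol*

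**What the plan says.** The first page of the protocol describes the 14 participants thus: "All participants are above the age of 18 and have been diagnosed with Normal Eustachian function". The objective is likewise confined to healthy people whose tubes work normally. The Study Design section adds "The design of the study was to be open and uncontrolled", and no dysfunction group or comparator is described.

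The Study Population section sets the entry rule: "Inclusion criteria included Individuals with normal eustachian function whose eardrum is intact and no hearing problems". Two lists of disqualifying conditions follow. One closes with "otosclerosis and those who had previous ear surgery were not included in the study group", the other with "If they had any of the conditions/disorders, they were disqualified from the study".

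The last bullet of that section turns to the ETDQ-7 questionnaire, which was "filled out in patients who came to the Otorhinolaryngology clinic of Haseki hospital and had various ear complaints". It continues: "Patients with a score of 14.5 points or greater in this quantitative test were accepted as potential 'chronic eustachian dysfunction patients". The rest of that sentence reports only that each such person then had audiology testing. The section ends there, at the heading Study Procedures.

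**The concern.** Three features make this look like a defect.

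- The only source of people described in the available text is a clinic population with ear complaints, and the only questionnaire threshold is one that flags suspected dysfunction. The target population is the opposite.
- The conditions in the two lists carry a stated consequence, whereas the ETDQ-7 cut-off carries none. Neither a questionnaire score nor Eustachian dysfunction appears in either list.
- The word *accepted* can be misread as *enrolled*.

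The stakes would be real if people with dysfunction had entered. The study concludes that the tube opens only when both paratubal muscles act together, and it concludes this for normal ears. With 14 participants analysed and no control group, each person is 1/14 = 7.1% of the sample, so a few misclassified participants could change what the result applies to. Short of that, two readers might decide differently on a high scorer whose tests turned out normal, and the entry rule could not be repeated exactly.

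**Working it through.** The protocol derives no figure on this point: 14.5 is a questionnaire threshold, not a calculated quantity. The check is therefore a comparison of the text.

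**Step 1: which statement governs entry.** Normal Eustachian function is required in the population row on the first page, in the objective, and in the first two bullets of the Study Population section. The inclusion bullet adds an intact eardrum and no hearing problems. All of these agree, and none mentions a questionnaire score. The rule is therefore a diagnosis, not a score.

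**Step 2: what the cut-off sentence does.** It classifies a person as a *potential* dysfunction patient and then reports audiology testing for all such people. To be accepted *as* something is to be classified as it; the sentence does not say that anyone was accepted *into* the study. Following the label with testing is how one describes a trigger for work-up, after which the diagnosis decides.

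**Step 3: where the two possible roles of the cut-off differ.** Assume that all other criteria are met.

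| ETDQ-7 score | Function on testing | Cut-off as trigger for testing | Cut-off as exclusion screen |
|---|---|---|---|
| below 14.5 | normal | eligible | eligible |
| below 14.5 | abnormal | not eligible | not eligible |
| 14.5 or more | abnormal | not eligible | not eligible |
| 14.5 or more | normal | eligible | not eligible |

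The readings agree in 3 of 4 cells. In the fourth, the person has been found to have normal function. Whichever reading is used, nobody without normal function enters, and the population in the objective is the population studied.

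**Step 4: whether silence in the lists matters.** The exclusion bullet names 10 conditions and the additional-factors bullet names 12, so 10 + 12 = 22 (21 if adenoid and other nasopharyngeal mass are counted as one). None is Eustachian dysfunction. That proves little. Dysfunction is already barred by the inclusion criterion and needs no second mention. Both lists are also introduced in non-exhaustive terms (*included*, *such as*). Comparing 22 diseases with one screening instrument sets unlike things side by side.

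**Step 5: what the participant account shows.** The closing section reports 16 people included, one lost to electrode dislodgment and one who refused the needle: 16 − 1 − 1 = 14. It describes no dysfunction group. It also states that every participant had a first tubometry test of tube opening on swallowing, so tube function was examined directly and not judged by questionnaire alone. The results of that first test are not given in the available text.

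**The case for a change.** The strongest case for raising the point runs as follows. Eligibility is protocol content and cannot be deferred to an analysis plan. The sentence is present and unclear, so this is more than a missing detail. The inclusion criterion settles confirmed dysfunction, but not the high scorer with normal tests. A sharper version calls the text a contradiction about who was enrolled, because the only recruitment route shown starts from people with complaints.

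Part of this stands. The section does not state what a score of 14.5 or more meant for entry, and a careful editor would have said so. It is also true that the available text does not spell out how normal function was diagnosed.

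The rest does not stand. The sharper version needs *accepted as* to mean *enrolled*, which the wording does not say and the population row on the first page rules out. The 7.1% per participant is only 1/14; it measures no misclassification, and nothing in the document shows any. The milder version needs the cut-off to work as an exclusion, which no sentence says. The idea that the sentence was carried over from another study has no support in the text. Finally, the copy reviewed lacks some passages, including the one directly after the Study Procedures heading. A description that breaks off at audiology testing may well continue there, and text absent for that reason cannot be counted as absent from the plan.

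**Conclusion.** The concern does not hold. The protocol states its entry rule consistently, as diagnosed normal Eustachian function with an intact eardrum and no hearing problems. The ETDQ-7 sentence describes a label and a referral for testing, and it neither contradicts nor replaces that rule. Its size is nil: no participant count, estimate or conclusion changes under either reading of the cut-off. The text reports a completed study, so no future enrolment decision depends on it either.

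This rests on two assumptions. The first is that *accepted as* means *classified as*, which is the natural sense. The second is that the statement that all participants had diagnosed normal function is accurate; nothing in the document speaks against it. An added sentence on the role of the cut-off would tidy the text but would change nothing the study did or concluded.

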A total of sixteen participants was included in the study with the gender distribution of 12 female and 4 male. The mean (SD) age of the subjects was 36.2 years (range 18-62 years). For one of the participants EMG recording was not obtained because of repetitive electrode dislodgment (possibly due to inadvertent swallowing activity). We attribute this failure to excessive saliva collected in the mouth. Another participant refused the needle insertion due to anxiety of needle fear. Thus, in 14 participants (mean age 36 years; 10 female and 4 male) EMG recordings with simultaneous tubometry data were obtained for both mLVP and mTVP.

Tubometry measurements were performed twice for every patient. First, the subjects were tested for the swallowing

efficacy of the ET opening. Second, the test was done withouwing activity while EMG activity of the muscles were recorded while observing ET openings on tubometry instrument. The measured pressure values obtained from the second test were used for calculating the amount of air entering or exiting the tympanic cavity.

The purpose of second tubometry testing was to observe and record the ET openings corresponding to concurrent EMG activities of the mLVP and mTVP with no swallowing action whatsoever. EMG and tubometry tests were performed and recorded by two different computers which were not linked to each other. Both instruments were started simultaneously at the same time to ensure synchronous operation. During the test, tubometry test device recorded pressure measurement of external ear canal only. Recording of nasal pressure is not done due to absence of swallowing activity. EMG recording device was operated in "continuous" mode where the data coming from the muscles were recorded continuously. Both EMG recordings and tubometry recordings were taken from the same ear undergoing the test. Analyses of the observed and recorded data revealed that only the double muscle activities of both mLVP and mTVP happening simultaneously were effective in opening ET. Isolated activities of either mLVP or mTVP were not effective for the ET openings in tubometry.

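### The conclusion that only combined mLVP and mTVP activity opens the Eustachian tube should be limited to openings that tubometry can detect

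*Protocol*

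**What the plan says.** The results text after the Study Procedures heading describes a second tubometry test, done without swallowing while EMG was recorded from both muscles. In that test the "tubometry test device recorded pressure measurement of external ear canal only", and "Recording of nasal pressure is not done due to absence of swallowing activity". The pressure values were "used for calculating the amount of air entering or exiting the tympanic cavity".

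Two conclusions follow. The first has no qualifier: "only the double muscle activities of both mLVP and mTVP happening simultaneously were effective in opening ET". The second does: "Isolated activities of either mLVP or mTVP were not effective for the ET openings in tubometry".

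Two other statements matter. General Information says of the tube that "its duty is to equalize the pressure inside the tympanic cavity with outside pressure". Study Population admits people with "normal eustachian function whose eardrum is intact and no hearing problems".

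**The concern.** The first conclusion is about the tube opening, whereas the measurement is of air exchange, seen indirectly as a pressure change on the outer side of an intact eardrum. The two coincide only when there is a pressure difference to release. If an isolated mLVP or mTVP event opened the tube while the pressures were equal, the trace would look the same as if the tube had stayed shut.

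The sentence matters because it answers the stated objective, which is to relate tube openings at rest to paratubal muscle function. Its negative half, that neither muscle opens the tube alone, is a claim about mechanism that others may take up as established.

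**Working it through.** The documents give no figure for this point that could be reproduced, so the check is one of reasoning from the protocol's own statements.

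**Inputs**

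1. Signal in the no-swallow test: external ear canal pressure only, with nasal pressure not recorded (results text after Study Procedures).
2. Use of the signal: calculation of air moving into or out of the tympanic cavity (same text).
3. Function of the tube: pressure equalisation (General Information).
4. Eardrum: intact (Study Population).
5. Participants with both EMG and tubometry: 14 (results text).
6. Number and timing of isolated and double events, pressure difference at each event, and detection limit: none in the visible text.

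**Steps**

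1. From inputs 1 and 2, an opening is recognised by air exchange, which appears as a change in ear canal pressure.
2. From input 3, air moves through an open tube when tympanic and outside pressure differ. If they are equal, no net air moves.
3. From input 4, the ear canal is closed off from the middle ear by the eardrum, so the signal depends on a change of middle-ear pressure. With no net air movement there is none to detect.
4. Let *o* be the chance that an isolated event opens the tube, and *d* the chance that such an opening shows in the ear canal trace. Assuming no signal without an opening, the share of isolated events with a signal is

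   *o* × *d*.

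   A share of zero is explained by *o* = 0 (isolated activity does not open the tube) or by *d* = 0 (it may open the tube, but nothing shows). The data decide between these only if *d* for isolated events is known to be well above zero.
5. Double events did produce recorded openings. For double events, therefore, both factors were above zero, and a pressure difference existed at least some of the time. This does not fix *d* for isolated events, which need not have met the same pressure differences. The difference is smallest just after an opening, so *d* can depend on when an event occurs.
6. From input 6, nothing in the visible text shows that isolated and double events met similar pressure differences.

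**Result.** The observation supported is that no air exchange was detected during isolated activity. The unqualified first sentence states more than this. The second sentence, which is tied to tubometry, does not go so far.

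**The case against.** The strongest reply is that the text qualifies itself. The sentence on isolated activity refers to openings in tubometry, the title and objective speak of air exchange, and the openings are described as those observed on the instrument. Read together, an opening could simply mean air exchange seen on tubometry. This largely stands, and it is why the point is small. It does not rescue the first sentence, which contains the word *only*, has no limit, and is the one most likely to be quoted alone.

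The second reply is that double events in the same test gave recorded openings, so the method could detect them. This stands as far as it goes. It shows that a pressure difference was present at some moments, not at each isolated event.

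The third reply is that part of the procedures text was not available to this review and may describe the tubometry conditions, including an applied or monitored pressure. This also stands. A known pressure difference imposed throughout the test would weaken the point considerably. For that reason, no omission is alleged.

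A reader might go further and infer that isolated activity does open the tube, that pressures were equal during isolated events, or that event timing explains the whole result. The documents support none of these. They give no timing of isolated against double events, no rate at which pressure builds up and no detection threshold. Any percentage put on missed openings would reflect only the inputs chosen.

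**Conclusion.** The point holds in a limited form. One sentence equates the absence of a recorded ear canal pressure change with the absence of an opening, and the signal described cannot establish that. The finding for double activity is not affected, nor is the second sentence as written. The conclusion that isolated activity cannot open the tube is neither shown to be wrong nor supported by the visible text.

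No numerical size can be attached. The conclusion rests on two assumptions: that openings were judged from the ear canal trace alone, as the results text indicates, and that the unavailable procedures text does not describe a known pressure difference at each isolated event. The matter is a minor correction of wording.

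**What to change.** Give the first sentence the limit that the next one already carries, for example: *only combined mLVP and mTVP activity was accompanied by air exchange detectable on tubometry; no external ear canal pressure change was recorded during isolated activity*. The second clause should be confirmed against the traces. Do not conclude that isolated activity cannot open the tube. The cost is one sentence and a weaker negative conclusion; no new data are needed.

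If a statement about opening itself is to be kept, use the recordings already held:

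- Compare isolated and double events at similar times since the previous muscle event of either kind, because an isolated event might itself have released pressure unseen.
- Let eligibility depend on that elapsed time only, never on what a later event shows. An isolated event that did open the tube could remove the signal from the next double event. Requiring that later signal would tend to discard the very openings being sought, and an upper limit calculated on what remained would not be valid.
- Analyse isolated mLVP and isolated mTVP separately.
- If few comparable isolated events exist, say that the effect of isolated activity was not tested.

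This optional step costs more. It needs a fixed definition of isolated and double activity, and alignment of traces from two computers that were not linked. Elapsed time is also only a stand-in for the pressure difference, so the comparison would make a claim about opening more credible without proving it.

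### The claim that only double muscle activity opens the tube is reported without an opening rate for time when neither muscle is active, so it is not shown to exceed chance coincidence

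*Protocol*

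**What the plan says.** Under Study Design the protocol states: "The design of the study was to be open and uncontrolled". Any control for the muscle claim must therefore come from within each recording.

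The results text after the Study Procedures heading gives the purpose of the second tubometry test, which was to "observe and record the ET openings corresponding to concurrent EMG activities of the mLVP and mTVP with no swallowing action whatsoever". The EMG device ran so that "the data coming from the muscles were recorded continuously". EMG and tubometry ran on two computers that were not linked but were started together.

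The conclusion is that "only the double muscle activities of both mLVP and mTVP happening simultaneously were effective in opening ET". The next sentence supplies the contrast: "Isolated activities of either mLVP or mTVP were not effective for the ET openings in tubometry". The text does not mention openings while both muscles were silent. It gives no number of openings, no number or duration of bursts of either type, no recording length and no rule for how close in time a burst and an opening must be to count as matched.

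**The concern.** To say that double activity was effective is to say that openings are more frequent during it than they would otherwise be. To say that only double activity was effective is to say also that openings do not occur in the other states. There are three kinds of time in the record: both muscles active, one active, neither active. The stated comparison uses the first two. An opening during the third would directly contradict 'only', and the rate in that third state is the natural background against which 'effective' should be judged.

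The stated purpose of the test adds to the concern, because it is framed around openings that accompany EMG activity. Background Information also treats the activity as recurring; of earlier EMG work it says that "these studies never revealed the periodic nature of the activity". Recurring bursts cover some share of the recording, so pressure events unrelated to the muscles would fall on them at about that share. Because the two computers were not linked, matching needs some time tolerance, and a tolerance widens that share.

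At stake is the study's central conclusion. Reading the two traces independently of each other would not settle it, since a reference rate would still be needed.

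**Working it through.** **Inputs from the protocol.** The number analysed is 14: 16 included, less 1 for electrode dislodgment and 1 refusal, 16 − 1 − 1 = 14. This agrees with "Thus, in 14 participants (mean age 36 years; 10 female and 4 male) EMG recordings with simultaneous tubometry data were obtained". Nothing else needed for the calculation is stated, so there is no figure of the protocol's own to reproduce on this point.

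**Assumptions.** Let d be the share of recording time in double activity (including the matching window), i the share in isolated activity, and m the number of openings over the whole study. Suppose openings are unrelated to muscle state and independent of one another. The conclusion covers all participants, so m is a study total: 14 for one opening each, 28 for two, 70 for five.

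**Case A: only openings that coincide with EMG activity are counted.** The chance that all m fall on double activity is (d/(d+i))^m.

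| Assumed d, i | d/(d+i) | m = 14 | m = 28 | m = 70 |
|---|---|---|---|---|
| 0.20, 0.02 | 0.20/0.22 = 0.909 | 0.26 | 0.07 | 0.001 |
| 0.20, 0.05 | 0.20/0.25 = 0.80 | 0.044 | 0.002 | 1.6 × 10⁻⁷ |

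More generally, let q = i/(d+i) be the isolated share of active time. The chance is (1 − q)^m. For m = 14 it is 0.87 at q = 1%, 0.49 at 5%, 0.23 at 10%, 0.044 at 20% and 0.00006 at 50%. For m = 50 it is 0.61 at 1%, 0.077 at 5% and 0.005 at 10%. It exceeds 0.05 only when q is below 1 − 0.05^(1/m), which is about 19% for m = 14, 10% for m = 28 and 3% for m = 100.

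**Case B: all openings are counted, including those with neither muscle active.** The chance that all m fall on double activity is d^m. For m = 14 this is 0.00006 at d = 50% and 5 × 10⁻⁸ at d = 30%. It exceeds 0.05 only when d is above 0.05^(1/14) = 0.81.

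**Share of chance openings in quiet time.** With d = 0.20 and i = 0.02, quiet time is 1 − 0.20 − 0.02 = 0.78 of the record. Ten burst-matched openings would imply 10/0.22 ≈ 45 in all, so about 35 with neither muscle active.

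**Reading.** In Case A chance is a live explanation if isolated activity is rare and openings are few. In Case B it is a poor explanation over most of the range. The text does not say which way of counting was used, nor give the counts that would place the study in either range.

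**The case against.** In plain reading, 'only' excludes openings in every other state, including the silent one. EMG was recorded continuously while openings were observed on tubometry, so quiet-time openings could have been seen. The sentence on the purpose of the second test does not say that unmatched openings were discarded. If they were looked for and none was found, Case B applies and chance is an implausible explanation for most values of d. Counts and definitions may also stand in a SAP or in parts of the protocol not available here.

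Much of this stands, and it rules out several stronger conclusions that a reader might draw:

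- That double bursts were the commoner type. Background Information describes a tight amplitude and delay relationship between the two muscle signals, which fits that picture, but no frequency is given.
- That chance would produce the same result. It would do so only if quiet-time openings were dropped and isolated activity was rare; otherwise many openings would have appeared in quiet time.
- That quiet time was never examined. This would be an inference from silence.
- That the finding is an ordinary chance result. Openings must be summed over 14 participants, and even at d = 0.20 and i = 0.02 five openings each gives about 0.001.

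The objection does not supply the missing reference. The protocol does not merely leave an analysis to be specified elsewhere. It states an absolute conclusion and names a contrast that omits the silent state.

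**Conclusion.** The concern holds in a limited form. The conclusion uses 'only' and 'effective', the contrast named is double against isolated activity, and no opening rate with neither muscle active is used as a reference. The text therefore does not show that the association exceeds chance coincidence. It does not follow that the association is due to chance.

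The size of the risk cannot be determined from the document. The illustrative probabilities rest wholly on assumed shares of recording time, assumed numbers of openings, and independence between openings. They show that the answer depends on counts the text does not give. Since those counts could either strengthen the conclusion considerably or overturn the word 'only', the re-analysis should be done.

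**What to change.** Use the continuous records already made.

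1. Before recounting, fix a matching tolerance between EMG and tubometry that allows for start offset and drift between the two unlinked computers.
2. For each participant, divide the second test into four states: both muscles, mLVP only, mTVP only, neither. Count all openings and the recording time in each, including openings with no EMG activity.
3. Compare each participant's rate during double activity with the same participant's neither-active rate and isolated rate, by a signed-rank test over the 14 participants. A participant with no isolated activity has no isolated rate and drops out of that comparison, so state the number used.
4. Do not rely on circular time shifts of the EMG as the sole null. For a periodic signal the shifts realign at each period and do not give distinct null arrangements.
5. Keep 'only' if no openings occurred in the neither-active or isolated states, and report those counts with the time observed. Otherwise write that openings were more frequent during double activity, if the comparison supports it.

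The cost is some re-analysis, provided the stored traces can be aligned, and a change to two sentences. No new participants or measurements are needed. The downside is that the conclusion may become less absolute; if the quiet and isolated states prove empty of openings, it becomes much stronger.

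### The stated conclusion sorts events only by whether one or both muscles were active, so as worded it cannot separate co-activation from contraction strength

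*Protocol*

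**What the plan says.** The Objectives section sets an observational aim: "This study focuses on the relationship between eustachian tube openings at rest and paratubal muscle functions". Study Design adds: "The design of the study was to be open and uncontrolled".

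Under Study Procedures, the results text describes a second tubometry test, done without swallowing, while the EMG of both muscles was recorded continuously. Recordings from 14 participants were obtained for both muscles. The text then concludes that "only the double muscle activities of both mLVP and mTVP happening simultaneously were effective in opening ET", and that "Isolated activities of either mLVP or mTVP were not effective for the ET openings in tubometry".

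These two statements come with no burst amplitude, no amplitude level at which a signal counts as activity, and no number of isolated events, double events or openings. Amplitude is mentioned in Background Information, where earlier EMG studies are said to have missed "the tight relationship between the two muscle signals in terms of amplitude and delay".

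**The concern.** The contrast between double and isolated events was not created by the investigators. The second test watched whatever the muscles did at rest, and nothing shown says that contractions were imposed or graded. Event type and contraction strength can therefore vary together. If a muscle fires harder when its partner also fires, two explanations predict the same record: the tube stayed shut because the partner was silent, or because the one active muscle was weak.

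The wording leaves no room for the second explanation. The word *only*, and the description of isolated activity as *not effective*, invite the reader to conclude that joint action is required. A tube that one muscle could open alone, above some force threshold, would give the same observation if isolated bursts seldom reached that threshold. What is at stake is the reading of the study's central result, not a number in the protocol.

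**Working it through.** **No figure to reproduce.** The protocol gives no amplitude, burst count or opening rate for this result. The one related count agrees with the text: 16 included − 1 electrode failure − 1 refusal = 14.

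**What the text allows.**
- Study Design: open and uncontrolled, so the comparison of event types is not protected by design.
- Second test: activity observed without swallowing, so strength was not set by the investigators in anything shown.
- Conclusion: event type only, so strength is not held constant in the statement.
- EMG recorded continuously, so amplitude should be recoverable.

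**Can weaker bursts alone give the pattern? (All inputs assumed.)** Suppose only one muscle matters and the other contributes nothing. Its amplitude is lognormal with log-SD 0.4 and median 1 in double events, and the tube opens above T = 1.0. In isolated events the median is r. Then

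P(opening | isolated) = P(Z > ln(T/r)/0.4), and P(opening | double) = P(Z > 0) = 50%.

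The chance of seeing no opening in n independent isolated events is (1 − p)^n. The values of n are assumed too: 20 is about 1.4 per participant over 14 participants, and 280 is 20 per participant.

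| r | ln(1/r)/0.4 | p, isolated | no opening, n = 20 | n = 100 | n = 280 |
|---|---|---|---|---|---|
| 1.0 | 0 | 50% | about 0 | about 0 | about 0 |
| 0.75 | 0.719 | 24% | 0.5% | about 0 | about 0 |
| 0.5 | 1.733 | 4% | 43% | 1.4% | about 0 |
| 0.3 | 3.010 | 0.1% | 97% | 88% | 69% |

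**A second assumed model.** Drive is normal with SD 0.3, mean 1.0 in isolated and 2.0 in double events, and the threshold is 1.6.
- Isolated: P(Z > (1.6 − 1.0)/0.3) = P(Z > 2) = 2.3%.
- Double: P(Z > (1.6 − 2.0)/0.3) = P(Z > −1.33) = 90.9%.
- No opening among isolated events: 0.97725^20 = 63%, 0.97725^100 = 10%, 0.97725^280 = 0.2%.

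**Reading.** Strength alone can produce the reported pattern, but only with a large deficit in isolated bursts or with few isolated events. At equal strength the difference disappears under the one-muscle model. A comparison at like amplitude would therefore tell that model from a need for both muscles, and the missing event counts matter as much as the missing amplitudes.

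**The case against.** The strongest reply is that two summary sentences do not show what the analysis did. The text says that analyses of the recorded data led to the result; it does not describe how bursts were detected, graded or compared. Parts of the protocol and any SAP were not available for this review, and an amplitude-matched comparison could sit there. A reader might infer from the text that the investigators disregarded contraction strength, or that isolated bursts were in fact weaker. The documents support neither inference: they report no amplitudes and do not say that amplitude was left out.

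A reader might also take "tight relationship between the two muscle signals in terms of amplitude and delay" as a commitment that the results text then breaks. It is not. The sentence says what earlier studies failed to reveal. It neither says that amplitude governs opening nor fixes an analysis.

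The reply has two further parts. As a description of spontaneous resting activity, the statement about isolated events may be true even if those bursts were weak; the aim is a relationship, and the protocol does not claim in so many words that one muscle could never suffice. And the illustrations assume the strength gap that is in question. At a ratio of 0.75 isolated bursts would still open the tube 24% of the time, and nothing shown points to a larger gap.

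All of this stands and narrows the point. It does not rescue the wording. The conclusion is drawn in the protocol itself, without qualification and without the figures that would let a reader rule out the alternative.

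**Conclusion.** The point holds as a limit on what the stated conclusion supports. As worded, it cannot separate the effect of joint activity from the effect of contraction strength, because it compares events by type alone in an uncontrolled observation. It is not shown that isolated bursts were weaker, that the analysis left strength out, or that the conclusion is false.

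No size can be derived from the documents. On assumed inputs, with a second muscle that contributes nothing, the isolated opening rate runs from 50% at equal strength to 0.1% at a ratio of 0.3, against 50% in double events. The chance of seeing no isolated opening ranges from essentially nil to 97%, depending on the strength ratio and the number of events. No single value in that range should be quoted as the effect. The point warrants a cheap addition to the analysis and a narrower sentence, and it does not call for new data.

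**What to change.** 1. From the recorded EMG and tubometry, report for each participant the number of isolated mLVP, isolated mTVP and double events, their amplitudes, and the openings that followed each type.
2. Compare opening rates at like amplitude within participant, for example with a logistic model containing both muscles' amplitudes, event type and a participant effect. If events are too few for a model, compare descriptively within the amplitude range that the event types share.
3. Limit the statement that isolated activity was not effective to spontaneous resting activity within the amplitude range actually observed. If isolated bursts do not reach the amplitudes at which double events opened the tube, say that one muscle's ability to open it alone was not tested.
4. If such an analysis already exists elsewhere, cite it beside the conclusion.

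The cost is further analysis of existing recordings and a reworded conclusion. EMG and tubometry were recorded on two unlinked computers started together, so event matching depends on that common start. EMG amplitude is only a proxy for force, overlap in amplitude may be sparse in 14 participants, and the conclusion may become less absolute. If amplitudes do overlap and isolated bursts still fail to open the tube, the conclusion becomes stronger.
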